This randomized, controlled, double-blind clinical trial was approved by the Ethics Committee of Izmir Katip Celebi University (Approval No: 14/100). Informed consent was obtained from parents, and the study adhered to CONSORT guidelines. A total of 200 healthy children (ASA I), aged 6–12 years, each with two fully erupted permanent mandibular first molars (400 teeth), were enrolled. Using a split-mouth design, one molar received a high-fluoride glass ionomer-based sealant (Fuji Triage, GC Corp., Tokyo, Japan; control), while the contralateral molar was treated with either a CPP-ACP-containing sealant (Fuji VII EP, GC Corp.) or a nano-fluorohydroxyapatite-based sealant (GCP Glass Seal, GCP Dental, The Netherlands). Sample size was calculated using G*Power 3.1.9.7, assuming an effect size of 0.40, $\alpha = 0.05$, and power = 0.80, yielding a minimum of 88 teeth per group. Considering a 15–20% potential loss, the final sample included 400 teeth. Inclusion criteria comprised children demonstrating cooperative behavior (Frankl scores 3–4) and having deep fissures without caries (ICDAS II; DIAGNOdent ≤ 15). Exclusion criteria included systemic disease (ASA $\geq II$), uncooperative behavior, enamel defects, or inability to attend follow-ups. Bitewing radiographs excluded proximal caries. Two calibrated examiners (Cohen's $k \geq 0.8$) conducted the study. Screening of 295 children included health history, caries risk assessment (Cariogram software, Malmö University), and inclusion of those with moderate caries risk. Randomization was two-phased: material pairing (Fuji Triage–GCP Glass Seal / Fuji Triage–Fuji VII EP) was determined using an online randomizer, while tooth allocation (right/left) was assigned by coin toss. Blinding was maintained for participants and evaluators. Before sealant application, baseline data (age, sex, oral hygiene, ICDAS II, and DIAGNOdent scores) were recorded. Teeth were cleaned and isolated; materials were applied per manufacturers' instructions. For Fuji materials, cavity conditioner was used for 10 s, followed by sealant placement, coating, and 20 s LED curing. GCP Glass Seal involved EDTA cleaning, 60 s light-curing, and surface coating with GCP Gloss. All restorations were inspected for marginal adaptation and polymerization, and occlusion was adjusted. Oral hygiene instructions were provided. Follow-up evaluations were conducted at 3, 6, 12, 18, and 24 months by a blinded examiner. Retention, marginal integrity, discoloration, and secondary caries were assessed using modified USPHS criteria. Retention was graded (1 = complete, 2 = partial, 3 = total loss); further caries evaluation (ICDAS II and DIAGNOdent) was performed for scores 2–3.

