
STATİSTİCAL ANALYSIS PLAN

Data were analyzed using IBM SPSS v21. Descriptive statistics were expressed as mean \pm SD or percentage. Normality was assessed with the Kolmogorov–Smirnov test. Non-parametric tests (Friedman, Kruskal–Wallis with Bonferroni correction) were used where appropriate. Categorical data were analyzed using Fisher-FreemanHalton, Pearson chi-square, or Fisher’s exact tests. Kaplan–Meier curves and log-rank tests compared material survival. Statistical significance was set at $p < 0.05$.

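### Follow-up ICDAS II and DIAGNOdent are described only for teeth that lost sealant, and the caries outcome covering all teeth has no paired between-material test

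*Combined protocol and SAP*

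**What the plan says.** All follow-up assessments are in the unnumbered protocol text. Before treatment, "baseline data (age, sex, oral hygiene, ICDAS II, and DIAGNOdent scores) were recorded", with no restriction to a subset. At follow-up, "Retention, marginal integrity, discoloration, and secondary caries were assessed using modified USPHS criteria", again with no restriction. The retention scale is the selection variable: "Retention was graded (1 = complete, 2 = partial, 3 = total loss". The only description of ICDAS II and DIAGNOdent after baseline is that "further caries evaluation (ICDAS II and DIAGNOdent) was performed for scores 2–3".

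On design: "Using a split-mouth design, one molar received a high-fluoride glass ionomer-based sealant", and the contralateral molar received one of two test materials.

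The Statistical Analysis Plan ties one method to an outcome: "log-rank tests compared material survival". The others are generic. "Categorical data were analyzed using Fisher-FreemanHalton, Pearson chi-square" or Fisher's exact tests, and "Non-parametric tests (Friedman, Kruskal–Wallis with Bonferroni correction) were used where appropriate". No primary endpoint, analysis set or between-material caries comparison is named. None of the categorical tests listed is paired.

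**The concern.** Randomisation makes the treated teeth comparable. It does not make the teeth that later lost sealant comparable. If one material loses more sealant, its score 2–3 teeth are a broader slice of its teeth than the other material's. If teeth prone to loss are also prone to caries, the two slices differ in susceptibility even when the materials do not. Selection can also break the pairs, because one molar of a child may be read and the other not.

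DIAGNOdent is the only plainly numeric follow-up measure described, so it is a natural target for the SAP's rank tests. A caries claim resting on these teeth could show a difference that does not exist or hide one that does.

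The available alternative, USPHS secondary caries, would be tested as if the two molars of a child were independent. That gives the wrong standard error for a split-mouth comparison.

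**Working it through.** The plan gives no figure on this point to reproduce, and no sealant-loss or caries rates. All rates below are assumptions chosen for illustration. In steps 1 to 3, loss means sealant loss (score 2–3).

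**1. What a comparison of the teeth read estimates.** Caries per randomised tooth = loss × caries in lost teeth + (1 − loss) × caries in retained teeth. Assume loss of 30% v 60% and caries in 20% of lost teeth for both materials. The teeth read show 20% v 20%. Per randomised tooth:
- no caries in retained teeth: 0.30 × 0.20 = 6.0% v 0.60 × 0.20 = 12.0%;
- 5% in retained teeth: 0.060 + 0.70 × 0.05 = 9.5% v 0.120 + 0.40 × 0.05 = 14.0%.

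The first comparison correctly describes teeth that lost sealant. It does not answer which material leaves more teeth carious.

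**2. False difference.** Assume true caries of 15% with both materials and loss of 30% v 60%. Link loss and caries through a bivariate normal with correlation r. Caries among teeth read = P(loss and caries) / P(loss). For r = 0.5: 0.0915 / 0.30 = 30.5% and 0.1314 / 0.60 = 21.9%.

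Rejection rates come from simulating 100 complete pairs, which assumes that the 200 children split evenly over the two pairings (the ratio is not stated). Ranges cover within-pair correlation 0 and 0.5. The rank test is a two-group test on a continuous reading at 0.05/3, approximating the stated Bonferroni correction for three materials.

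| r | Expected caries among teeth read | Chi-square, nominal 5% | Rank test at 0.05/3 |
|---|---|---|---|
| 0 | 15.0% v 15.0% | 3–5% | at most about 2% |
| 0.3 | 23.8% v 19.3% | 6–9% | 2–5% |
| 0.5 | 30.5% v 21.9% | 13–16% | 8–11% |
| 0.7 | 38.2% v 24.0% | 28–30% | 28–30% |

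With 2,000 runs, simulation error at a 30% rate is 1.96 × √(0.3 × 0.7 / 2000), about 2 percentage points. At 20% v 40% loss the chi-square rejects 4–5%, 5–7%, 9–11% and 18–19%. At equal loss of 30% there is no material inflation at any r.

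**3. Unpaired test on all teeth.** Take caries of 15% in both molars and an assumed within-pair correlation of 0.5 on the underlying normal scale. Then P(both carious) = 0.0577, and the correlation of the yes/no outcomes is (0.0577 − 0.15²) / (0.15 × 0.85) = 0.276. The true standard error of the difference is √(1 − 0.276) = 0.851 of the one that the chi-square uses. The effective critical value is 1.96 / 0.851 = 2.30, so a nominal 5% test rejects about 2.1% of the time; simulation gives 2–3%. The unpaired test is conservative, and the cost is power.

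**4. Drop-out.** The protocol allows for 15–20% loss. From 100 pairs that leaves 100 × 0.85 = 85 to 100 × 0.80 = 80. At 80 pairs and r = 0.7, the chi-square on teeth read rejects 23–25%.

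**5. The replacement.** If USPHS detects only a fraction d of lesions under intact sealant, observed caries = P(loss and caries) + d × (0.15 − P(loss and caries)). With d = 0.5 and r = 0: 0.045 + 0.5 × 0.105 = 9.75% v 0.090 + 0.5 × 0.060 = 12.0%. McNemar's test then rejects 6–9% over r from 0 to 0.7, and 5–6% if d is 75–100%.

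**The case against.** The plan states no caries comparison on score 2–3 teeth. It presents those readings as an addition to USPHS caries, and any short SAP that leaves endpoints unnamed permits many poor tests. This stands: the text supports only that the test is not excluded. A reader might infer that such a comparison was planned or carried out, or that the trial's caries result is biased. The documents say neither.

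A false difference needs three things together: the test is run, loss is unequal, and loss is linked to susceptibility. Enrolment was narrowed to moderate caries risk, cooperative healthy children and sound fissures, which plausibly weakens the link without excluding it. With 20% v 40% loss and r = 0.3, the chi-square is close to nominal. This also stands.

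An uncorrected two-group rank test would reject about 47% of the time at r = 0.7, and it is tempting to quote that figure. It ignores the SAP's Bonferroni correction, so it overstates what the written plan would produce.

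A reader might also expect unpaired tests to inflate false positives. With positive within-pair correlation they do the reverse.

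Finally, the replacement is not better in every setting. At r = 0 with 50% detection, McNemar's test on USPHS caries is worse than the chi-square on teeth read; at r = 0.3 the two are about equal. That limits the remedy. It does not make the selected teeth a randomised comparison.

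**Conclusion.** The concern holds in limited form. The documents establish that follow-up ICDAS II and DIAGNOdent are described only for teeth selected by a post-randomisation outcome, that the SAP does not exclude a between-material test on them, and that the caries outcome without this restriction is left to unpaired tests in a split-mouth trial.

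The size of any distortion cannot be derived from the documents. Under the assumed 30% v 60% loss and 15% caries, it runs from none without a link to 28–30% rejection at r = 0.7 with 100 complete pairs, and less with fewer pairs or a smaller gap in loss. The unpaired test on all teeth rejects about 2–3% at an assumed within-pair correlation of 0.5. The gap in the plan is certain and the harm is conditional, so this should be corrected, with medium confidence in its practical effect.

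**What to change.** In the SAP:

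- Name modified USPHS secondary caries, scored on every randomised tooth, as the between-material caries comparison.
- Analyse it within pairs and separately for each pairing, in place of the unpaired tests: for example, McNemar's test at 24 months on complete pairs. Report the number of incomplete pairs, with a sensitivity analysis for the expected 15–20% loss.
- State whether the ICDAS II and DIAGNOdent readings feed the USPHS score.
- Tabulate USPHS caries by material and retention score, with a sensitivity analysis over assumed detection under intact sealant.
- Report ICDAS II and DIAGNOdent among score 2–3 teeth descriptively, with the number of teeth read per material and visit. Base no caries claim on them.

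The cost is SAP wording, one table and the sensitivity analyses; no new measurements are needed. The SAP is written in the past tense, so if outcomes have already been analysed, the choice must be dated and labelled post hoc. The downside is that USPHS scoring may miss lesions under intact sealant, so unequal retention can still affect the result. The change reduces the problem and does not remove it.

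### Power is stated at alpha 0.05, but the Kruskal–Wallis follow-up comparisons carry a Bonferroni correction that the stated power does not reflect, and three materials do not need so strict a method

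*Combined protocol and SAP*

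**What the plan says.** The sample-size sentence of the protocol text gives an effect size of 0.40 and alpha 0.05, "and power = 0.80, yielding a minimum of 88 teeth per group". It names the software ("Sample size was calculated using G*Power 3.1.9.7") but not the test, the endpoint, the type of effect size or the sidedness. The next sentence reads "Considering a 15–20% potential loss, the final sample included 400 teeth".

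There are three materials. Every child has one control tooth, and "the contralateral molar was treated with either a CPP-ACP-containing sealant (Fuji VII EP, GC Corp.) or a nano-fluorohydroxyapatite-based sealant". The ratio of the two pairings is not stated.

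The Statistical Analysis Plan lists "Kruskal–Wallis with Bonferroni correction" among the non-parametric tests, next to Friedman, for use where appropriate. It gives no divisor, no adjusted level and no list of corrected comparisons. The overall threshold is p < 0.05. No correction is stated for the log-rank or categorical tests, and no primary analysis is named.

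**The concern.** A significant Kruskal–Wallis test over three materials says only that they are not all alike. Within that family, the corrected pairwise tests say which material differs. The size was worked out at an uncorrected 0.05, and nothing in the plan links the two levels. A reader would take 0.80 as the chance of detecting a pairwise difference of the assumed size, when the corrected tests have less.

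Some of that loss is avoidable. For exactly three groups, Holm or a closed procedure also controls the family-wise error and gives up less power than Bonferroni.

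**Working it through.** **Inputs.** From the protocol text: effect size 0.40, alpha 0.05, power 0.80, 88 teeth per group, 15–20% loss, 400 teeth in 200 children. Assumed, because not stated: 0.40 is a standardised mean difference d; tests are two-sided; the pairings are 1:1, so 200 control teeth and about 100 per new material; Bonferroni divides by the three pairs, 0.05/3 = 0.0167.

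**1. The plan's own figure.** For two groups, n = 2[(z₀.₉₇₅ + z₀.₈₀)/d]² = 2[(1.960 + 0.842)/0.40]², which is 99 per group (100 with the t distribution). The 88 is not reproduced. Other readings miss it too: one-sided 78; two-sided Wilcoxon–Mann–Whitney 104 (normal) or 91 (logistic); three-group analysis of variance 22 at f = 0.40 or 82 at f = 0.20. The 88 therefore does not show which test was powered.

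**2. Accept 0.80 at 0.05 and change only the level.** Power = Φ(z₀.₉₇₅ + z₀.₈₀ − z₁₋α′/₂).
- Three pairs, α′ = 0.0167: Φ(1.960 + 0.842 − 2.394) = Φ(0.408) = 0.66.
- Two pairs, α′ = 0.025: Φ(1.960 + 0.842 − 2.241) = Φ(0.560) = 0.71.

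Holding 0.80 at 0.0167 multiplies the size by [(2.394 + 0.842)/(1.960 + 0.842)]² = 1.33, so 88 becomes about 118 per group. This step does not need d or the endpoint, only a two-sided single contrast.

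**3. Power at d = 0.40 for the trial's numbers.** Two-sample noncentral t, noncentrality d√[n₁n₂/(n₁ + n₂)], teeth treated as independent. Loss of 15–20% leaves 100 × 0.85 = 85 to 100 × 0.80 = 80 teeth per new material, and 170 to 160 control teeth.

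| Comparison | Teeth | Noncentrality | Power at 0.05 | Power at 0.0167 |
|---|---|---|---|---|
| Stated size | 88 v 88 | 2.65 | 0.75 | 0.59 |
| New v new, full enrolment | 100 v 100 | 2.83 | 0.80 | 0.66 |
| New v new, 15% loss | 85 v 85 | 2.61 | 0.74 | 0.58 |
| New v new, 20% loss | 80 v 80 | 2.53 | 0.71 | 0.55 |
| Control v new, full enrolment | 200 v 100 | 3.27 | 0.90 | 0.80 |
| Control v new, 15% loss | 170 v 85 | 3.01 | 0.85 | 0.73 |
| Control v new, 20% loss | 160 v 80 | 2.92 | 0.83 | 0.70 |

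After loss, Bonferroni costs new v new about 0.16 (0.74 − 0.58; 0.71 − 0.55). The remaining 0.06–0.09 below 0.80 comes from size and loss. Under this reading, 0.80 at 0.0167 needs 133 per group.

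**4. What a less strict valid method recovers.** With three groups, once one pair truly differs at most one pairwise null can be true. An omnibus test at 0.05 followed by each pair at 0.05 is therefore a closed procedure. Simulations, d = 0.40 for one new material:
- 160/80/80 independent teeth, new v new: Bonferroni 0.53, Holm 0.57, closed 0.64.
- 88 per group, independent teeth: about 0.56 with Bonferroni, about 0.67 closed. Closed family-wise error was 0.036–0.050 across the null and partial-null settings.
- Split-mouth (paired) data, new v new: Bonferroni 0.50, Holm 0.56, with family-wise error at or near 5%.

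**The case against.** **The 0.0167 is not in the plan.** This stands. A reader might infer that the SAP tests three pairs at 0.0167, but no divisor or list of pairs is given, and the correction may also concern Friedman comparisons between visits. The mismatch does not hang on a divisor of three, since two pairs already bring 0.80 down to 0.71.

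**These may not be the deciding tests.** This stands too. It is tempting to say that the stated power fails the comparisons that settle the trial. The documents do not support that. The one sentence that expressly compares materials concerns survival by log-rank, and graded outcomes may go to chi-square or exact tests; neither carries a stated correction. DIAGNOdent, the clearly numeric follow-up measure, is repeated only for retention scores 2–3, so 80–88 teeth per group would not apply to it.

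**The powered test may have been the omnibus test.** The figure of 88 cannot settle this. The omnibus readings give 22 or 82, but the two-group d = 0.40 reading gives 99–100. Failure to reproduce 88 excludes neither. If the omnibus test was powered, the plan gives no power for the pairwise tests.

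**Power may be adequate.** In part. Control v new has 0.80 at full enrolment. If 0.40 is a within-child paired effect (equal to d = 0.40 at a correlation of 0.5), 80–100 pairs give 0.87–0.94 at 0.0167. If it is Cohen's f, the size is also ample. Pairing does not rescue new v new, because each child receives only one new material.

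**Bonferroni is valid, and a later change could look data-driven.** Both are true. The plan is inefficient here, not wrong, and the documents are written in the past tense, so timing has to be disclosed.

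**Conclusion.** The concern holds in a limited form. The stated power is for alpha 0.05 and does not describe Bonferroni-corrected Kruskal–Wallis follow-ups. A contrast truly powered at 0.80 would have about 0.66 over three pairs or 0.71 over two.

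Under d = 0.40, 1:1 pairing, independent teeth and the planned loss, new v new is the weak comparison at 0.55–0.58. Control v new is at 0.70–0.73, and better if pairing is used. A reader might blame the whole drop from 0.80 to 0.59 at 88 per group on the correction; that overstates it, because 88 gives only 0.75 before any correction.

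The finding is confined to the Kruskal–Wallis family. Confidence is medium, because the test, effect-size type, sidedness, divisor and pairing ratio are all unstated.

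**What to change.** 1. State which comparisons are corrected and with what divisor, and whether the Friedman comparisons are included.
2. For material comparisons in the Kruskal–Wallis family, replace Bonferroni by Holm, which is never less powerful and holds under any dependence between the tests. The alternative is the closed procedure: omnibus at 0.05, then each pair at 0.05. The closed version's gain was simulated above on independent teeth, whereas the design is split-mouth. Omnibus and pairwise tests must therefore respect the child, with paired tests for control v new.
3. Restate power for each pairwise contrast at the level at which it is tested, naming the test, the effect-size type and the numbers after loss.

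The cost is a sentence or two in the SAP and a restated power. There are four downsides. Matching simultaneous intervals are less simple. The closed version allows pairwise claims only after a significant omnibus test. New v new still does not reach 0.80 (0.56–0.57 with Holm, 0.64 closed, in the simulations above). If the data have already been seen, the change must be reported as post hoc, with the Bonferroni results alongside.

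### The analysis plan assigns no paired or clustered method to the within-child comparison of each test sealant with Fuji Triage, so the listed tests are conservative and waste power if a child's two molars are positively correlated

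*Combined protocol and SAP*

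**What the plan says.** The unnumbered protocol text sets out the pairing: "Using a split-mouth design, one molar received a high-fluoride glass ionomer-based sealant", and the opposite molar received one of the two test sealants. There were 200 children, "each with two fully erupted permanent mandibular first molars (400 teeth), were enrolled". Which pairing a child received "was determined using an online randomizer"; within the child, "tooth allocation (right/left) was assigned by coin toss".

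The Statistical Analysis Plan section then lists tests by type of data:

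- Categorical outcomes: "Categorical data were analyzed using Fisher-FreemanHalton, Pearson chi-square", or Fisher's exact test.
- Other outcomes: "Non-parametric tests (Friedman, Kruskal–Wallis with Bonferroni correction) were used where appropriate".
- Survival: Kaplan–Meier curves, and "log-rank tests compared material survival".

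The section does not mention McNemar, signed-rank or marginal homogeneity tests, conditional logistic regression, GEE or mixed models, or any stratified, clustered or frailty form of survival analysis. It does not say which test serves which contrast.

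**The concern.** Each test sealant is compared with the Fuji Triage molar in the same mouth. The two molars share diet, hygiene, caries risk, behaviour during placement and probably the operator, so their outcomes are likely to be positively correlated. Tests for independent groups ignore that covariance.

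With positive correlation the error is conservative. The estimated difference is unchanged when both molars are observed, but its standard error is too large. A real difference between a test sealant and Fuji Triage is then more likely to be reported as non-significant than under the paired analysis that the design allows. Readers may take such a result to mean that the materials perform alike.

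Fuji VII EP versus GCP Glass Seal is a comparison between different children, and unpaired tests are valid there.

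**Working it through.** **Inputs from the documents.** 200 children with two molars each; effect size 0.40 (type not stated); alpha 0.05; power 0.80; "yielding a minimum of 88 teeth per group"; 15–20% loss; visits at 3, 6, 12, 18 and 24 months.

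**Assumptions.** Within-child correlation ρ, failure rates and an equal split of children between pairings (100 and 100) are not given, so a range is shown for ρ and examples for the rest.

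**The plan's own figure.** Read as a standardised mean difference, 0.40 at 80% power needs 100 per group two-sided or 78 one-sided in a two-sample t-test. The stated 88 is not reproduced; at 88 the two-sided power is 75%. This is a separate matter. Below, 88 and 0.40 serve only as an illustration.

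**Step 1: size of the unpaired test within a pairing.** The true variance of the difference is (1 − ρ) times the variance under independence. The standard error is therefore overstated by 1/√(1 − ρ), and the true two-sided size is 2[1 − Φ(1.96/√(1 − ρ))].

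| ρ | SE ratio | True size at nominal 5% |
|---|---|---|
| 0 | 1.00 | 5.0% |
| 0.1 | 1.05 | 3.9% |
| 0.3 | 1.20 | 1.9% |
| 0.5 | 1.41 | 0.6% |

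**Step 2: power, 88 pairs, standardised difference 0.40.** The standardised signal is 0.40 × √(88/2) = 2.653. In the normal approximation:

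- unpaired power = Φ((2.653 − 1.96)/√(1 − ρ))
- paired power = Φ(2.653/√(1 − ρ) − 1.96)

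At ρ = 0.3, √0.7 = 0.837. Unpaired: Φ(0.693/0.837) = Φ(0.83) = 80%. Paired: Φ(3.171 − 1.96) = Φ(1.21) = 89%. Simulation with t-tests (40,000 runs) gives slightly lower values:

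| ρ | Unpaired | Paired |
|---|---|---|
| 0 | 75% | 75% |
| 0.1 | 77% | 79% |
| 0.3 | 79% | 88% |
| 0.5 | 83% | 96% |

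**Step 3: binary outcome, assumed failure 40% v 25%.** The per-pair variance of the difference is 0.24 + 0.1875 − 2φ√(0.24 × 0.1875) = 0.4275 − 0.4243φ. At φ = 0.31 this is 0.296, so the unpaired standard error is √(0.4275/0.296) = 1.20 times the true one. Simulated power (40,000 runs; McNemar asymptotic, without continuity correction):

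| φ | 88 pairs: chi-square v McNemar | 100 pairs: chi-square v McNemar |
|---|---|---|
| 0 | 57% v 56% | 63% v 62% |
| 0.18 | 58% v 65% | 64% v 70% |
| 0.31 | 59% v 74% | 65% v 79% |
| 0.46 | 59% v 84% | 67% v 88% |

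The exact versions behave alike: with 88 pairs, Fisher's exact stays at 50% while exact McNemar gives 50/57/66/77%. In a null check (30% v 30%, 100 pairs, latent correlation 0.3/0.5/0.7), the size is 3.1/1.8/0.7% for chi-square and 5.2/5.3/5.4% for McNemar.

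**Step 4: log-rank at the five visits.** 100 pairs, assumed control failure 8/15/25/33/40% by visit, no dropout, 20,000 runs. For power, 24-month failure is 40% v 25%, a hazard ratio of ln(0.75)/ln(0.60) = 0.563.

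| Latent correlation | Size: unpaired v child-clustered | Power: unpaired / child-clustered / pair-stratified |
|---|---|---|
| 0.1 | 4.2% v 4.9% | 63 / 64 / 59% |
| 0.3 | 2.6% v 4.7% | 64 / 72 / 65% |
| 0.5 | 1.5% v 5.1% | 66 / 80 / 74% |
| 0.7 | 0.5% v 5.0% | 68 / 90 / 87% |

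At zero correlation the powers are 62.5%, 61.7% and 56.3%, so stratifying by pair costs power when correlation is low.

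**Step 5: three materials with controls pooled.** With an assumed 200/100/100 teeth, the size of Kruskal–Wallis is 4.5%, 3.3% and 2.2% at ρ = 0.1, 0.3 and 0.5. Pooling weakens the effect but does not remove it.

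**The case against.** The strongest reply is that the error is on the safe side. It invalidates no positive finding, and its cost depends on a correlation the documents never state: nil at 0, about two percentage points at 0.1 (77% v 79%), and large only at higher values. This is correct, and the actual loss in this trial is unknown. But conservative p-values do not support a conclusion of no difference, and the mismatch affects categorical and survival comparisons with the control.

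Four further points have some force.

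- *Unpaired power does not fall as correlation rises.* In these calculations it holds or rises slightly. The loss is relative to a paired analysis of the same data.
- *Friedman is a related-samples test.* Within one pairing it reduces to a sign test and could be applied to the ordered retention grade. But the plan gives it no such role, no child received all three materials, and it does not serve the survival comparison or the outcomes assigned to chi-square and Fisher-type tests. Its use across visits is the likelier reading, though that is an inference.
- *A sample size in teeth does not show that pairing was ignored.* Each child has one tooth per material, so within a pairing 88 teeth per group is also 88 pairs. No weight is placed on it here.
- *The 100-pair powers ignore dropout.* With an equal split, 15–20% loss leaves 85 to 80 pairs. Absolute power is then lower but the gap remains: at 80 pairs and a standardised difference of 0.40, unpaired v paired power is 73% v 75%, 75% v 85% and 79% v 94% at ρ = 0.1, 0.3 and 0.5.

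**Conclusion.** The concern holds. The design pairs each test sealant with Fuji Triage within the child, while the plan assigns categorical outcomes to independent-sample tests and survival to an ordinary log-rank test. Whenever a child's molars are positively correlated, the resulting standard errors and p-values are too large. At a correlation of 0.3 the standard error is about 20% too large, the true size is about 2% instead of 5%, and power is about 9 points lower than with pairing (79% v 88%) in the illustration with 88 pairs. The loss is about 2 points at 0.1 and 13 at 0.5.

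The direction follows from the design and needs only a positive correlation. The sizes rest on assumed correlations, failure rates and an equal split between pairings, and on reading 0.40 as a standardised mean difference. Type I error is not inflated, estimates from complete pairs are unaffected, and Fuji VII EP versus GCP Glass Seal is outside the criticism.

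**What to change.** Revise the Statistical Analysis Plan so that each contrast has a named method:

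- **Each test sealant v Fuji Triage, within its own pairs.** Binary outcomes: McNemar or conditional logistic regression. Ordered retention and USPHS grades: Wilcoxon signed-rank or marginal homogeneity. Survival: log-rank or Cox with variance clustered by child, which keeps nominal size and had more power than pair stratification in the simulations.
- **Any three-material comparison.** One GEE or mixed model per outcome, with child as the cluster.
- **Incomplete pairs.** The protocol assesses ICDAS II and DIAGNOdent at follow-up only for retention grades 2–3, so often only one molar of a pair will have a value. McNemar and signed-rank tests drop such pairs; the GEE or mixed model can use them. Name one primary method per outcome, since conditional and marginal models estimate different quantities.
- **Fuji VII EP v GCP Glass Seal.** Keep the unpaired tests.
- **Friedman.** State which outcome and which factor it is used for.

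The cost is rewording and a re-analysis of existing data, with no new patients or measurements.

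### No primary outcome, visit or material contrast is designated, and no stated rule controls the error rate across outcomes, visits, or the categorical and log-rank tests

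*Combined protocol and SAP*

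**What the plan says.** The protocol text describes a split-mouth trial of three materials. Each child is assigned one of two pairings, both containing the control Fuji Triage: "Randomization was two-phased: material pairing (Fuji Triage–GCP Glass Seal / Fuji Triage–Fuji VII EP) was determined using an online randomizer".

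On outcomes and timing it states "Retention, marginal integrity, discoloration, and secondary caries were assessed using modified USPHS criteria" and "Follow-up evaluations were conducted at 3, 6, 12, 18, and 24 months by a blinded examiner". No outcome or visit is marked as primary. The sample-size sentence does not supply one either: it gives an effect size of 0.40, α = 0.05 and power 0.80, with the result stated as "yielding a minimum of 88 teeth per group", but without an outcome, visit, test or contrast.

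The Statistical Analysis Plan gives one significance level, "Statistical significance was set at $p < 0.05", and three sentences on tests:

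- The first, on rank-based methods, reads "Non-parametric tests (Friedman, Kruskal–Wallis with Bonferroni correction) were used where appropriate".
- The second turns to the graded and yes/no outcomes, again without naming any of them: "Categorical data were analyzed using Fisher-FreemanHalton, Pearson chi-square, or Fisher’s exact tests".
- The third, on how long the sealants last, says only this: "Kaplan–Meier curves and log-rank tests compared material survival".

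Only the first mentions an adjustment. There is no hierarchy, split of alpha or gatekeeping rule. The plan does not say whether the categorical and log-rank tests compare the materials two at a time or all three at once.

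**The concern.** Without a designated primary comparison, any isolated p-value below 0.05, for any outcome, visit or material, meets the plan's stated criterion, except where the Bonferroni correction applies. A reader cannot tell a planned finding from the most favourable of many looks.

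The gap falls where the main results are likely to come from. Graded USPHS scores lend themselves to the categorical tests, and sealant survival goes to the log-rank tests. Neither sentence states an adjustment. At stake is whether a claim that one sealant outperforms Fuji Triage carries a 5% error rate or a much larger one.

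**Working it through.** **The plan's own figures.** The documents state no family-wise error rate, so there is none to reproduce. The one related figure, 88 teeth per group, cannot be verified because neither the test nor the type of effect size is given. A two-sample t test with d = 0.40, for example, needs 100 per group two-sided and 78 one-sided. That does not show 88 to be wrong. It is taken at face value below, for the cost only.

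**Inputs from the documents:** 4 outcomes, 5 visits, 2 pairings in different children, threshold 0.05, power 0.80, 200 children, 15–20% loss.

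**Assumptions:** two-sided tests; all null hypotheses true; the families listed; correlation 0.8 among tests within a pairing; within-child correlation r = 0.3 or 0.5; independent pairings.

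**1. Size of one test when pairing is ignored.** With positive within-child correlation r, the true variance of the difference is (1 − r) times what an unpaired test assumes. The actual size is 2[1 − Φ(1.960/√(1 − r))]:

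- r = 0.3: 1.960/√0.7 = 2.343, size 0.0191
- r = 0.5: 1.960/√0.5 = 2.772, size 0.0056

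**2. Small families at one outcome and one visit.**

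- One global test of three materials, correctly sized: 5%.
- Two pairwise contrasts, correctly sized: 1 − 0.95² = 9.75%.
- Two contrasts, unpaired: 1 − (1 − 0.0191)² = 3.8% at r = 0.3; 1 − (1 − 0.0056)² = 1.1% at r = 0.5.

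**3. Every outcome, visit and pairing.** 4 × 5 × 2 = 40 tests, 20 per pairing. For critical value k (1.960, 2.343 or 2.772), the chance of no rejection within a pairing is

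q = ∫ φ(u) [Φ((k − √0.8·u)/√0.2) − Φ((−k − √0.8·u)/√0.2)]²⁰ du,

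and over both pairings the family-wise error is 1 − q².

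| Tests used | 1 − q (one pairing) | 1 − q² (all 40) |
|---|---|---|
| Correctly sized | 22.4% | 39.8% |
| Unpaired, r = 0.3 | 10.4% | 19.6% |
| Unpaired, r = 0.5 | 3.7% | 7.2% |

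Weaker correlation raises these rates; 40 independent, correctly sized tests would give 1 − 0.95⁴⁰ = 87.2%. Exact tests with few events lower them.

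**4. Power cost of Holm over two contrasts.** At 88 per group the standardized effect is 1.960 + 0.842 = 2.802, so power is 0.800 at α = 0.05 and Φ(2.802 − 2.241) = 0.712 at α = 0.025. Under Holm a contrast succeeds if its p is below 0.025, or if its p is below 0.05 and the other's is below 0.025:

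- Both effects present: 0.712 + (0.800 − 0.712) × 0.712 = 0.775
- Other effect zero: 0.712 + (0.800 − 0.712) × 0.025 = 0.715 (0.7145 before rounding)

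An equal split of 200 children, which is assumed because no ratio is stated, gives 100 pairs per pairing. After 15–20% loss, 80–85 remain, below 88. Scaling 2.802 by √(n/88):

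| Pairs | Power at 0.05 | Power at 0.025 | Holm, both effects | Holm, other effect zero |
|---|---|---|---|---|
| 88 | 80.0% | 71.2% | 77.5% | 71.5% |
| 85 | 78.6% | 69.6% | 75.9% | 69.8% |
| 80 | 76.2% | 66.6% | 73.0% | 66.9% |

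**The case against.** **Bonferroni is in the plan.** This is partly right. On the ordinary reading it covers pairwise follow-up after Kruskal–Wallis, and ordinal retention scores could be analysed that way. It would be wrong to infer that every test is unadjusted at 0.05. But its family is undefined, it is unclear whether it also covers Friedman, and nothing carries it across outcomes, visits or the other two groups of tests.

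**Retention is obviously primary.** No sentence says so. The event behind material survival is also undefined; it could be partial or total loss. Inferring a primary from the results is what a designation should prevent.

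**The inflation is not demonstrated.** A reader might infer that the error must exceed 5%, or that 9.75% is the minimum. The documents support neither. A single global three-material test is a possible reading and carries 5%, and unpaired tests on positively correlated teeth can bring a small family below that. This objection stands as far as it goes. But conservatism of unknown size is not a control rule, and on the assumptions above it does not hold the 40-test family to 5%.

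**Pairing is a separate issue, and the work is already done.** Both points have some force. Pairing enters here because it sets the actual size of each test and because the split-mouth randomization makes within-child contrasts the natural primary. The plan is written in the past tense, so a primary named now may not restore prespecified error control.

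**Conclusion.** The point holds as an omission with consequences. The documents designate no primary outcome, visit or contrast, and they state no rule controlling the family-wise error beyond a Bonferroni correction of unclear scope. Testing everything listed at the stated threshold could yield a false claim with probability from about 7% to about 40%, under the 40-test family and correlations assumed above. A narrower analysis could carry 5% or less. The plan does not say which applies, so these figures illustrate the exposure and do not measure it. The omission is plain; only its numerical size is uncertain. It should be corrected. Estimates with confidence intervals remain usable in the meantime.

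**What to change.** 1. Name one primary outcome and time frame, for example retention to 24 months, with the failure event defined for the analysis.
2. Compare each test material with Fuji Triage within its own pairs, by a method that respects the pairing: for example a child-stratified log-rank test, or a marginal model with child-clustered standard errors.
3. Apply Holm over the two contrasts at an overall two-sided 0.05.
4. Report all other outcomes and visits, and the contrast between the two test materials, as secondary with 95% confidence intervals.
5. State which tests the Bonferroni correction covers.
6. If results are already known, label the primary as post hoc. It then limits selective claims but does not restore prespecified control.

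**Cost.** This takes plan wording and a paired re-analysis of data already collected, with no added enrolment. Some nominally significant results become descriptive. With the stated 80% power at 88 per group at face value, per-contrast power is about 77% if both materials have the planned effect and 71% if the other has none. With the 80–85 pairs left after the plan's own loss allowance, it is about 73–76% and 67–70%. The power of the paired test itself cannot be derived from the documents: a child-stratified log-rank, for instance, draws information only from pairs in which one tooth fails at an earlier visit than the other. The power statement should therefore be restated for the chosen outcome, test and contrasts.
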